13.5 Safety Analysis

Prior to analysis, all AEs will be coded using the MedDRA coding dictionary. Based on these coded terms, TEAEs and SAEs will be summarized using system organ class and preferred terms, as well as by relationship to treatment. All AEs will be listed, regardless of whether they were study treatment related.

Vital signs will be summarized using descriptive statistics (mean, standard deviation, median, minimum, maximum, and number of non-missing observations) by time point. Changes from baseline will also be summarized by post-dose time point.

Clinical laboratory parameters will be summarized using descriptive statistics (mean, standard deviation, median, minimum, maximum, and number of non-missing observations) by time point. Changes from baseline will also be summarized by post-dose time point. In

	MSK-003	Page 39
---	---------	---------

addition, a shift table will be constructed to show the shifts in laboratory results by parameter relative to the normal ranges. The number and percentage of subjects with the following shifts will be presented: normal/normal, normal/low, normal/high, low/low, low/normal, low/high, high/low, high/normal, and high/high. Similar shift tables will also be constructed for physical exam results. ECG results will be summarized in a shift table with the following shifts presented: normal/normal, normal/abnormal, abnormal/normal and abnormal/abnormal. A table of descriptive statistics for QTc will be created.

Additional safety analyses may be performed as described in the SAP for the study.

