2.2 Study Endpoints

2.2.1 *Safety Endpoint*

Safety endpoints of this study are:

- Incidence of patients experiencing treatment-emergent adverse events (TEAEs)
- Incidence of patients experiencing study drug-related TEAEs
- Incidence of patients experiencing equal or greater than Grade 3 TEAEs
- Incidence of patients discontinuing from the study due to TEAEs
- Physical exam and weight
- Vital signs including systolic blood pressure (SBP) and diastolic blood pressure (DBP), heart rate, respiration, and body temperature
- Clinical laboratory tests, including hematology, chemistry and urinalysis
- Concomitant medication review
- Electrocardiogram (ECG) parameters

2.2.2 *Efficacy Endpoint*

Efficacy endpoint of this study is change in MG-ADL score over time.

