3. STATISTICAL METHODS

3.1 General

All data will be analyzed using the Statistical Analysis System (SAS®; Version 9.2 or higher).

Continuous variables will be presented by descriptive statistics: n, mean, standard deviation, median, minimum, and maximum. Categorical variables will be tabulated by frequency count and percentage. No hypothesis testing will be performed.

3.1.1 *Display of Decimal Places*

Means and medians will be reported to one decimal place more than the original unit reported on the case report form (CRF) or by the laboratory/vendor. Standard deviations will be reported to two decimal places more than the original unit. Minimum and maximum values will be reported to the same number of decimal places displayed on the CRF or by the laboratory/vendor.

3.1.2 *Visit Windowing*

For Vital signs, ECG, Lab and physical exam, the following protocol-specified visits are further defined for summary tables as below.

- Screening Visit (Baseline): the day subject was screened following the ICF signing
- Follow-up visit (3 Months): the visit date was most close to 91 days after baseline visit.
- Follow-up visit (6 Months): the visit date was most close to 183 days after baseline visit.
- Follow-up visit (9 Months): the visit date was most close to 274 days after baseline visit.
- Follow-up visit (12 Months): the visit date was most close to 365 days after baseline visit.
- Follow-up visit (15 Months): the visit date was most close to 456 days after baseline visit.
- Follow-up visit (21 Months): the visit date was most close to 640 days after baseline visit.
- Follow-up visit (27 Months): the visit date was most close to 822 days after baseline visit
- Follow-up visit (33 Months): the visit date was most close to 1005 days after baseline visit
- Follow-up visit (39 Months): the visit date was most close to 1187 days after baseline visit

For completed subjects, Follow-up visit (39 Months) is considered End of study visit.

For discontinued subjects, if the assessments at the scheduled visit prior to the early termination (ET) visit were not done, the ET visit will be assigned as the prior scheduled visit. Otherwise, the ET visit will be assigned to the next scheduled visit.

Other visits will be listed as “Unscheduled Visits”, and data collected at unscheduled visits will not be included in the summary table, but will be presented in the data listings.

3.1.3 *Missing Data Handling*

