3.3 Safety Analysis

3.3.1 *General*

All safety summaries will be presented overall for the safety population. The evaluation will take into account the recorded adverse events (AE), clinical laboratory tests, vital signs, physical exam, ECG assessments and concomitant medications.

3.3.2 *Adverse Events*

Since patients started taking study medication before enrolled the study, all AE reported are considered as treatment-emergent adverse events (TEAE).

Tabular summaries will be provided by indication for the number and percentage of patients with:

- Any TEAE by SOC and PT. This summary will include the number of unique events reported.
- Any study drug-related TEAE by SOC and PT
- Any TEAEs by SOC, PT and maximum severity
- Any treatment-emergent serious adverse event (TESAE) by SOC and PT
- Any TEAE that results in patient discontinuation from the study by SOC and Preferred Term (PT)

A listing of all adverse events will be provided. In addition, separate data listings will be presented for the following:

- Patient deaths

- Serious Adverse Events (SAEs)
- Listing of Grade 3 (Severe) or Grade 4 (Life-threatening) AEs
- Listing of AEs leading to study discontinuation

3.3.3 *Vital Signs*

A summary of values and changes from Baseline will be provided by vital signs parameter and visit of at 3, 6, 9, 12, 15, 21, 27, 33 and 39 months.

3.3.4 *Electrocardiogram (ECG)*

Each over-read ECG interval and change from baseline in each interval will be summarized descriptively by visit at 3, 6, 9, 12, 15, 21, 27, 33 and 39 months

Treatment-emergent cardiac abnormalities, as well as the overall interpretation, will be summarized. Treatment-emergent ECG findings considered by the investigator to be clinically significant will be presented only in a listing.

3.3.5 *Clinical Laboratory Assessments*

A summary of laboratory values and changes from Baseline will be provided by test and visit of at 3, 6, 9, 12, 15, 21, 27, 33 and 39 months. In addition, laboratory measures out of range or abnormal will be presented for each visit. Values deemed clinically significant by the Investigator will not be summarized, but will be presented in a listing.

3.3.6 *Physical Examinations*

The number and percent of patients with physical examination abnormalities will be summarized by body system and visit of at 3, 6, 9, 12, 15, 21, 27, 33 and 39 months.

3.3.7 *Concomitant Medications*

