4. OUTPUT PLANNED FOR THE STUDY REPORTS

4.1 Tables Planned for Interim Reports and Final Study Report

| Table # | Table Title | CSR | DSUR |
|---------|--|-----|------|
| T01 | Subject Disposition (All subjects) | X | X |
| T02 | Demographics and Baseline Data Summary Statistics (Safety Population) | X | X |
| T03 | Summary of Study Drug Exposure and Compliance (Safety Population) | X | X |
| T06 | Number and Percent of Subjects with Treatment Emergent Adverse Events (Safety Population) | X | X |
| T07 | Summary of Treatment Emergent Adverse Events (Safety Population) | X | X |
| T08 | Number and Percent of Subjects with Treatment Emergent Serious Adverse Events (Safety Population) | X | X |
| T09 | Number and Percent of Subjects with Treatment Emergent Adverse Events by Relationship to Treatment (Safety Population) | X | X |
| T10 | Number and Percent of Subjects with Treatment Emergent Adverse Events of Grade 2 or Higher (Safety Population) | X | X |
| T11 | Serum Chemistry Clinical Laboratory Summary Statistics by Visit (Safety Population) | X | |
| T12 | Hematology Clinical Laboratory Summary Statistics by Visit (Safety Population) | X | |
| T13 | Urinalysis Clinical Laboratory Summary Statistics by Visit (Safety Population) | X | |
| T14 | Serum Chemistry Shift Table by Visit (Safety Population) | X | |
| T15 | Hematology Shift Table by Visit (Safety Population) | X | |
| T16 | Urinalysis Shift Table by Visit (Safety Population) | X | |
| T17 | Vital Sign Parameters Summary Statistics by Visit (Safety Population) | X | X |
| T19 | Summary of ECG by Assessment Category and Visit (Safety Population) | X | |
| T20 | ECG Shift Table by Assessment Category and Visit (Safety Population) | X | |
| T21 | Number and Percent of Subjects Taking Concomitant Medications by ATC Level 3 and Preferred Term (Safety Population) | X | |

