4.2 Listings Planned for Interim Reports and Final Study Report

| Listing # | Data Listing Title | CSR | DSUR |
|-----------|--|-----|------|
| DL01 | Subject Disposition Data Listing | X | X |
| DL02 | Protocol Deviations Data Listing | X | |
| DL03 | Demographics Data Listing | X | |
| DL05 | Prior and Concomitant Medications Data Listing | X | |
| DL06a | Adverse Events Data Listing | X | X |
| DL06b | Serious Adverse Events Data Listing | X | |
| DL06c | Adverse Events with Grade 3 or Higher Data Listing | X | |
| DL06d | Adverse Events Leading to Study Discontinuation | X | |
| DL07 | Physical Exam Data Listing | X | |
| DL08 | Vital Signs Data Listing | X | X |
| DL09 | ECG Data Listing | X | |
| DL10 | Study Drug Administration Data Listing | X | |

| | | | |
|------|------------------------------|---|---|
| DL11 | Serum Chemistry Data Listing | X | X |
| DL12 | Hematology Data Listing | X | X |
| DL13 | Urinalysis Data Listing | X | X |
| DL15 | Pregnancy Test Data Listing | X | |

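### The SAP drops the protocol's physical examination shift table without declaring it, so no planned summary table separates findings new since extension entry from those already present

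*SAP*

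**What the plan says.** Protocol 13.5 describes laboratory shift tables relative to the normal range and then adds: "Similar shift tables will also be constructed for physical exam results". It also plans a normal/abnormal shift table for ECG.

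SAP 2.2.1 names "Physical exam and weight" among the safety endpoints. SAP 3.3.6 gives the analysis: "The number and percent of patients with physical examination abnormalities will be summarized by body system and visit", with the visits written as "visit of at 3, 6, 9, 12, 15, 21, 27, 33 and 39 months". It mentions no change or shift from baseline.

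SAP 4.1 lists shift tables for chemistry, hematology, urinalysis (T14 to T16) and ECG (T20). It has no physical examination table under any number. SAP 4.2 has one relevant entry, DL07, "Physical Exam Data Listing", marked for the study report only.

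SAP 3.6, the section for departures from the protocol's analysis, declares only that the MG-ADL analysis is dropped. Protocol 13.7 says that where the two documents differ, the SAP governs and no amendment is issued.

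**The concern.** Long-term safety is the primary objective, and physical examination is one of the named safety endpoints. The useful question for a patient in an extension study is whether a body system that was normal at entry has become abnormal. A shift table answers it. A count of abnormal patients at each visit does not, because it mixes persisting findings with new ones. It also depends on which patients are still being seen: follow-up runs to Month 39 and SAP 3.1.3 imputes nothing.

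There is an internal gap as well. Even the simpler summary promised in SAP 3.3.6 has no table in SAP 4.1. A programming team working from the output list would produce DL07 and nothing else for this endpoint.

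**Working it through.** The documents give no figure to reproduce: there is no sample size calculation, test or margin. The check is a comparison of the texts, followed by a bound on what a visit count can tell the reader.

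**Step 1. What the SAP keeps of the shift tables in Protocol 13.5**

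| Domain | Protocol 13.5 | SAP 3.3 text | SAP 4.1 |
|---|---|---|---|
| Laboratory | Shift table | Values, change from baseline, abnormal values by visit | T11 to T13 summaries; T14 to T16 shift tables |
| ECG | Shift table | Intervals, change from baseline, treatment-emergent abnormalities | T19 summary; T20 shift table |
| Physical examination | Shift table | Abnormal counts by visit, no baseline comparison | None |

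The SAP text does not mention shift tables for laboratory tests or ECG either, but SAP 4.1 supplies them. Physical examination is the only domain where the promised shift table appears nowhere. The vital signs paragraph shows that the SAP asks for a baseline comparison when it wants one: "A summary of values and changes from Baseline will be provided by vital signs parameter".

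**Step 2. What a visit count identifies**

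Take *n* patients examined at both baseline and a visit, with *b* abnormal at baseline and *a* abnormal at the visit. The number abnormal at both times lies between max(0, *a* + *b* − *n*) and min(*a*, *b*). Subtracting from *a*:

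newly abnormal lies between max(0, *a* − *b*) and min(*a*, *n* − *b*).

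If *b* is unknown, this widens to 0 to *a*.

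The documents give no abnormality rates, so the counts below are assumptions. The values of *n* are the planned group sizes (about 60 MuSK-MG and about 10 AChR-MG patients), with everyone still followed.

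| *n* | *a* | *b* unknown | *b* = *a*/2 | *b* = *a* | *b* = 2*a* |
|---|---|---|---|---|---|
| 60 | 6 | 0 to 6 | 3 to 6 | 0 to 6 | 0 to 6 |
| 60 | 12 | 0 to 12 | 6 to 12 | 0 to 12 | 0 to 12 |
| 60 | 18 | 0 to 18 | 9 to 18 | 0 to 18 | 0 to 18 |
| 10 | 2 | 0 to 2 | 1 to 2 | 0 to 2 | 0 to 2 |

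For *n* = 60 and *a* = 12, the unknown-*b* range is 0/60 to 12/60, or 0% to 20% of patients. In this grid a baseline count alone narrows the range only when *b* is below *a*. Unless one of the two counts is 0 or *n*, it does not give a single value. The cross-tabulation gives the number directly.

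**Step 3. Other routes to the same information**

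- DL07 lists examinations by patient. Its contents are not specified. If it includes the baseline examination, a reader could build the comparison by hand.
- Protocol 8.6.6 has clinically significant changes from baseline on examination recorded as adverse events. Changes not judged clinically significant are not captured.
- SAP 3.3.2 and 3.5 count every reported adverse event as treatment-emergent, and Protocol 9.1 includes non-serious events that began under MSK-002. The adverse event tables therefore do not separate new events from carried-over ones.

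**The case against.** The strongest reply is that the important findings are not lost. A clinically significant change on examination becomes an adverse event and is tabulated and listed, and DL07 carries the patient-level data. The protocol's leading safety measure is the incidence of treatment-emergent adverse events, with physical examination as a supporting assessment. The study is uncontrolled, descriptive and tests no hypothesis, and Protocol 13.7 allows the SAP to differ without an amendment. All of this stands. It limits the consequence but does not explain why this one shift table disappears, undeclared, while the others are kept.

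Four stronger readings might be inferred, and the documents do not support them:

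- **That new abnormalities cannot be detected at all.** DL07 and the adverse event reports may reveal some of them.
- **That the SAP excludes a baseline column.** SAP 3.1.2 says "For Vital signs, ECG, Lab and physical exam, the following protocol-specified visits are further defined for summary tables as below", and its list includes a baseline visit. The vital signs and laboratory paragraphs use the same Months 3 to 39 list while reporting change from baseline. The missing cross-tabulation is clear; a missing baseline column is not.
- **That a shift table would show what emerged on treatment.** SAP 3.3.2 states that patients were already taking study medication before enrolling. The table would show change since entry to the extension.
- **That abnormal findings at entry are known to be common.** This is plausible in MG, since the examination covers eyes, respiratory and musculoskeletal systems, but neither document gives a rate.

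The missing number T18 is also not evidence of a deleted table, because T04 and T05 are absent too.

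**Conclusion.** The point holds as a protocol-to-SAP mismatch with a limited but real cost. The planned shift table is replaced by visit counts, those counts have no table in the output list, and the change is not declared. As written, no summary table can give the number of patients newly abnormal since extension entry. From a visit count of *a*, that number is anywhere from 0 to *a*. The bound is arithmetic and needs no assumption about MG; its size in this trial depends on abnormality rates that the documents do not give.

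No test or primary conclusion turns on this. It should be corrected because the SAP as written gives a poorer answer on a named safety endpoint than the protocol promised, and the remedy is simple.

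**What to change.** - In SAP 3.3.6, restore the shift table: baseline normal or abnormal against each visit's normal or abnormal, by body system and by MG type (in line with SAP 3.1.4), among patients with both assessments. Show that denominator at each visit.
- Add the table to SAP 4.1.
- Label it as change since the MSK-003 baseline, not since a drug-free state.
- Confirm that baseline examinations taken from MSK-002 are in the analysis database. Protocol Table 1 allows them to be used, whereas SAP 3.1.2 ties baseline to the screening day after consent.
- If the table is left out on purpose, say so in SAP 3.6 with the reason, and reconcile 3.3.6 with 4.1.

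The cost is a few lines of SAP text and one table shell. The examinations are already scheduled at entry and at every visit, so no new collection is needed provided the MSK-002 baseline records are available.

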3.4 Analysis Report

Multiple interim analyses may be conducted upon requested. For example, the annual development safety update report (DSUR) and/or 120 Day safety update. The final study report will be conducted after study completed. One database lock is planned for this study at the end of the study.

3.5 Key Data Items

Study Analysis Population Definition:

- All Subjects: All subjects, including screening failures, who provided clinical information in the database.
- Safety Population: All enrolled subjects who receive at least one dose of study drug.

Important Derived Variables:

- Age (in year) = (Screening Date – Date of Birth +1)/365.25.
- Prior Medications and Treatments: The medications and treatments started before enrolled to the study (date of Informed Consent signed)
- Concomitant Medication and Treatments: The medications and treatments started on or after the date of Informed Consent signed
- Baseline: All safety measurements collected at Day 1 or before the first dose of study drug will be used as baseline
- Post Baseline Visit: follow up visit of 6, 9, 12, 15, 21, 27, 33 and 39 months after baseline and etc, or unscheduled visit after first dose of the study drug
- Study Day for follow-up visit: The visit date – Baseline date +1
 - o Follow-up visit at 3 months: The visit that is closest to study day 91
 - o Follow-up visit at 6 months: The visit that is closest to study day 183
 - o Follow-up visit at 12 months: The visit that is closest to study day 365
 - o Follow-up visit at 15 months: The visit that is closest to study day 456
 - o Follow-up visit at 21 months: The visit that is closest to study day 640
 - o Follow-up visit at 27 months: The visit that is closest to study day 822
 - o Follow-up visit at 33 months: The visit that is closest to study day 1005
 - o Follow-up visit at 39 months: The visit that is closest to study day 1187
- Duration of Disease (year):
(Date of Informed Consent signed – Date of original Diagnosis +1) / 365.25
- Study drug compliance (%): $100 \times \text{Total Dose (mg)} / \text{Total Prescribed Dose (mg)}$, where total dose taken will be calculated as (Dispensed # - Retuned # - Lost #) $\times 10$ mg (refer to CRF IP Accountability page (DA domain), and the total prescribed dose is collected at each IP accountability CRF (EX domain))
- Treatment emergent Adverse Events (TEAE): All AEs reported in this study are TEAE

Formulas of Metric Conversion:

- 1 inch = 2.54 cm
- 1 lb = 0.4536 kg
- $^{\circ}\text{C} = (^{\circ}\text{F} - 32) \times 5/9$

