1.2 Design

The study will enroll those patients who have completed the MSK-002 study and after all final evaluations for that study have been completed, or those who demonstrated benefit after completing the dose titration period but failed to meet the randomization criteria on Day 0 of MSK-002.

The duration of participation for each patient is expected to be at least 9 months as patients may continue in the study until amifampridine is approved by Regulatory Agencies or the clinical development of amifampridine is terminated for this indication. In addition to amifampridine, patients will continue to receive previous concomitant medications, as needed.

After a new informed consent is signed and inclusion / exclusion criteria for the current protocol are satisfied, eligible patients will be given the optimal dose and dosing schedule that was identified in the Run-in Period from Protocol MSK-002.

The findings from the physical exam (including vital signs, weight); 12-lead ECG; clinical laboratory test results (including pregnancy testing) and any ongoing adverse events will be used as the baseline for the long-term safety evaluation.

The only efficacy measurement is the MG-ADL which will be completed every 3 or 6 months. Safety and tolerability assessments will be made every 3 or 6 months or more frequently at the discretion of the Investigator. The study will continue until amifampridine is approved by Regulatory Agencies or until development of the product for this indication is halted or until month 39 is reached. The Investigator may alter the dose and dosing frequency during the Long-Term Study as well as schedule additional clinic visits for any reason.

Patients will be seen in the clinic at the end of Months 3, 6, 9, 12, 15, 21, 27, 33 and 39. In between the 3-or 6-month visits, patients may also have telephone/video contact with the site, or unscheduled visits, if needed.

Any unused medication must be brought back to the clinic at each visit for drug accountability, and an additional supply will be dispensed.

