In general, all categories that appear on the CRF and in summary table templates will be reported even if no patients reported that category (e.g., if there are no patients of a particular race). The “Missing” category displayed for categorical variables in summary table templates will only be displayed if missing observations are present. If no observations meet the criteria for inclusion in a data display (e.g., if there are no SAEs), the table or listing will be generated with a line in the body of the listing such as “None reported.”

No imputation will be conducted for the missing data.

3.1.4 *Sub-group Analyses*

All safety endpoints will be analyzed by MG type: MuSK-MG and AChR-MG.

3.2 *Subject Disposition, Demographics, Baseline Characters and Study Drug Compliance*

3.2.1 *Patient Disposition*

Study completion status will be summarized for all patients. The duration of treatment will be summarized for treated patients. Categories summarized will include patients who were planned, screened, screen failure, enrolled, received study drug, completed the study, were lost to follow-up, or withdrew early. Reasons for screen failure and withdrawal will be summarized.

3.2.2 *Protocol Deviations*

Individual protocol deviations will be presented in a data listing.

3.2.3 *Demographics and Baseline Characters*

Demographic characteristics of all patients enrolled will be summarized descriptively. The summary will include age, gender, race/ethnicity, height, weight.

3.2.4 *Study Drug Exposure*

The treatment duration (day), the total dose (mg) of study drug administered, average daily dose of study drug, and study drug compliance (%) will be tabulated.

- Treatment Duration (day) is calculated as The Last Dose Date – The First Dose Date +1. If the last dose date is missing, then the last visit date will be used.
- Total Dose (mg) will be calculated as the sum of the daily dose (mg) over the Treatment Duration, considering different doses during individual time periods within the study, as documented in the IP Accountability eCRF page.
- Average Daily Dose (mg) will be calculated as Total Dose (mg) / Treatment Duration (day). This will be calculated considering each time period and Daily dose during that period, as documented in the IP Accountability eCRF page.
- Study Drug Compliance (%): $100 \times \text{Total Dose Taken (mg)} / \text{Total Dose Prescribed (mg)}$

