A detailed listing of any concomitant medication taken by a patient during the course of the study will be provided. All medications, including those taken prior to study drug administration, will be listed by indication and sorted by patient and medication start date.

The following summaries will be provided by drug class and WHODRUG preferred term:

- Prior medications (medications started prior to taking study medication),
- Concomitant medications (medications started during study treatment),
- Ongoing medication (medications given during treatment, and still ongoing after completed study).

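### SAP 3.5 and 3.3.7 define concomitant medication by start date only, with different anchors, so by definition T21 counts new starts and not all on-treatment use

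*SAP*

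**What the plan says.** The SAP classifies medications in two places.

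- SAP 3.5 (Key Data Items) anchors on consent. Prior is "The medications and treatments started before enrolled to the study (date of Informed Consent signed"); concomitant is "The medications and treatments started on or after the date of Informed Consent signed".
- SAP 3.3.7 (Concomitant Medications) anchors on study drug. It promises three summaries by drug class and preferred term: "Prior medications (medications started prior to taking study medication"), "Concomitant medications (medications started during study treatment") and "Ongoing medication (medications given during treatment, and still ongoing after completed study"). It also says "All medications, including those taken prior to study drug administration, will be listed"; DL05 in SAP 4.2 is that listing.

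SAP 4.1 lists one medication table, T21. Its title refers to subjects taking concomitant medications, by ATC level 3 and preferred term. No table title is given for the prior or ongoing summaries.

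On background therapy, SAP 1.2 states that "patients will continue to receive previous concomitant medications, as needed", and protocol 8.1 says the same. Protocol 8.4 bases CRF recording on use during the Long-Term study, not on start date. The opening sentence of SAP 3.3.7 likewise speaks of concomitant medication in terms of use over the course of the study.

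**The concern.** In an extension study, most background treatment can be expected to predate entry, and the design says that it continues. A definition that looks only at the start date puts that treatment under *prior*, even when the patient takes it alongside amifampridine. A table titled for subjects taking concomitant medications would then show only drugs started after entry.

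Concomitant medication review is a listed safety endpoint (SAP 2.2.1), and the protocol synopsis says that these data will be summarized. Protocol 8.4 asks for caution with drugs that prolong QTc. Under the written definitions, a patient who entered already on such a drug is not counted in T21, while a patient who starts one on treatment is.

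Because the two sections use different anchors, two programmers could each follow the SAP and produce different versions of T21. The rule in protocol 13.7 that the SAP prevails does not settle this, since both definitions are in the SAP.

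**Working it through.** No figure in the plan is at issue, so the check applies each definition to the possible orderings of a drug's start and stop against consent, first MSK-003 dose, last dose and study end. SAP 3.3.7 is read in two ways. SAP 3.3.2 says that patients were already on study medication before enrolling, so it is unclear whether the study medication in 3.3.7 means MSK-003 dosing only or includes MSK-002 dosing.

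| Drug | SAP 3.5 | 3.3.7, MSK-003 anchor | 3.3.7, MSK-002 anchor | Taken on MSK-003 treatment? |
|---|---|---|---|---|
| 1. Started before any amifampridine, stopped before first MSK-003 dose | prior | prior | prior | no |
| 2. Started before any amifampridine, stopped during MSK-003 treatment | prior | prior | prior | yes |
| 3. Started before any amifampridine, still used after study completion | prior | prior + ongoing | prior + ongoing | yes |
| 4. Started during MSK-002 dosing, before MSK-003 consent, stopped during MSK-003 treatment | prior | prior | concomitant | yes |
| 5. Started between consent and first MSK-003 dose, stopped during treatment | concomitant | prior | concomitant | yes |
| 6. Started and stopped during MSK-003 treatment | concomitant | concomitant | concomitant | yes |
| 7. Started after last dose | concomitant | none | none | no |

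Three things follow.

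1. **Omission.** Drugs 2 and 3 are taken on treatment but are not concomitant under any reading. Drug 4 is also omitted, except under the MSK-002 anchor. If T21 follows the definitions, it leaves these drugs out.
2. **What the other summaries recover.** The Ongoing category has no start-date condition, so it captures drug 3. It does not capture drug 2, which appears only under prior. Prior has no stop-date condition, so there drug 2 is mixed with any drug of type 1. The three categories also overlap, because drug 3 is in two of them and one patient can contribute to several. Adding them does not give the number of patients on a drug during treatment.
3. **Conflict between sections.** Drugs 5 and 7 are classified differently by 3.5 and by 3.3.7 with the MSK-003 anchor. Drug 4 is classified differently if the MSK-002 anchor is used. Protocol Table 1 puts consent and treatment in one column, so the interval for drug 5 is probably short.

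**The case against.** The strongest reply is that little is lost. DL05 lists every medication. SAP 3.3.7 promises prior and ongoing summaries as well as the concomitant one. SAP 4.1 also omits titles for other promised summaries (physical examination, TEAEs leading to discontinuation), so a missing title does not show that a summary will be dropped. No table shell is given for T21, and the word *taking* in its title could be read as use. The study is descriptive, and no planned analysis links medication to ECG findings. Showing background drugs apart from new starts is a reasonable display.

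Much of this stands, and it rules out some stronger readings that a reader might infer:

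- That a drug taken throughout MSK-003 and still used after study completion vanishes from every summary. It does not; the Ongoing summary covers it.
- That the range of on-treatment use can be worked out from the prior and concomitant counts alone. It cannot. For C patients in the concomitant summary and O in the ongoing summary for one drug, the on-treatment number is at least max(C, O). A range that ignores O does not describe what the planned summaries leave open.
- That T21 will certainly omit carried-over drugs. That is what the written definitions imply; without a shell it is not an established outcome.

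The reply does not remove the core problem. A listing is not a count, drugs carried in and stopped on treatment have no summary of their own, and the two SAP sections disagree.

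**Conclusion.** The point holds as a defect of definition. By the SAP's own wording, T21 shows drugs started after entry, yet its title and the documents' use of *concomitant* elsewhere invite the reader to take it as total on-treatment use. The content of the table also depends on which section is programmed.

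The size cannot be stated, because the documents give no medication frequencies, start dates or stop dates. The harm is limited to one descriptive safety table: no data are lost, and no other planned analysis uses the classification. The conclusion assumes that T21 is programmed from the stated definitions and, for 3.3.7, that study medication means MSK-003 dosing. Under the MSK-002 anchor, drugs started before MSK-002 are still omitted. The definitions should be corrected before programming because this is cheap and the study's primary purpose is safety.

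**What to change.** Use one definition in both SAP 3.3.7 and 3.5:

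- **Concomitant:** taken on at least one day from first to last MSK-003 dose, that is, started on or before the last dose, and stopped on or after the first MSK-003 dose or ongoing.
- **Prior:** stopped before the first MSK-003 dose.
- State that study medication, for this purpose, means MSK-003 dosing.

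In T21, give the on-treatment total and show continued and newly started drugs separately. This keeps the distinction that the present definitions make.

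The cost is two reworded definitions, a date-overlap flag and a slightly longer T21. The flag relies on stop dates or an ongoing indicator; protocol 8.4 already asks for discontinued medications to be recorded on the CRF.

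Two optional items would tidy the text but are not part of the error. One is a classification rule for partial dates, since SAP 3.1.3 says "No imputation will be conducted for the missing data". The other is to align the table list in SAP 4.1 with the summaries promised in 3.3.7.
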